## 8.2.2 Exclusion Criteria

1. History of any illness or condition that, in the opinion of the investigator, might confound the results of the study or pose an additional risk in administering ivacaftor to the subject
2. An acute upper or lower respiratory infection, or pulmonary exacerbation, or changes in therapy (including antibiotics) for pulmonary disease within 4 weeks of Day 1
3. Known colonization with organisms associated with a more rapid decline in pulmonary status (e.g., *Burkholderia cenocepacia*, *Burkholderia dolosa*, and *Mycobacterium abscessus*). A subject is excluded if they have a positive culture of one of these organisms.
4. Abnormal liver function at screening or any prior history of clinically relevant elevated ( $>2 \times$  upper limit of normal [ULN]) serum aspartate transaminase (AST), serum alanine transaminase (ALT), or bilirubin (excluding newborn hyperbilirubinemia, e.g., physiologic jaundice or breastmilk jaundice of the newborn)
5. Hemoglobin  $<9.5$  g/dL at screening
6. History of solid organ or hematological transplantation
7. Any clinically significant “non-CF-related” illness within 2 weeks of Day 1. “Illness” is defined as an acute (serious or nonserious) condition (e.g., gastroenteritis)
8. Use of any moderate or strong inducers or inhibitors of cCYP3A within 2 weeks of Day 1
9. Participation in a clinical study involving administration of either an investigational or a marketed drug within 30 days or 5 terminal half-lives (whichever is longer or as determined by the local requirements) before screening. Note: Participation in a noninterventional study (including observational studies, registry studies, and studies requiring blood collections without administration of study drug) is permitted.
10. Chronic kidney disease of Stage 3 or above
11. Unable to undergo an adequate slit-lamp examination at screening
12. Presence of a lens opacity or cataract identified at the screening OE (excluding those considered congenital and nonprogressive, such as a suture cataract)

## 8.3 Observational Arm

### 8.3.1 Inclusion Criterion

1. Completed ivacaftor treatment in Study 124 Part B and elected not to enroll in the ivacaftor arm of Study 126, or received at least 1 dose of ivacaftor and prematurely discontinued ivacaftor treatment in Study 124 Part B and received at least 1 dose of ivacaftor treatment in Study 124 Part B

### 8.3.2 Exclusion Criterion

1. Receiving ivacaftor treatment

## 9 STUDY IMPLEMENTATION

### 9.1 Overview of Study Design

[figure not shown]
This is a Phase 3, 2-arm, multicenter study.

Enrollment in Study 126 is closely linked to Study 124 which will enroll subjects according to defined age cohorts, starting with ages 12 to <24 months, followed sequentially by appropriately grouped descending age cohorts based on available PK data.

This study includes an ivacaftor arm (open-label, 96-week treatment period) and an observational arm. The study design is shown in Figure 9-1.

**Figure 9-1 VX15-770-126 Study Design**

- a For subjects who have a Same-day Transition, the Week 24 visit of Study 124 Part B will be the same day as the Day 1 Visit of Study 126. For subjects who have a Gap Transition, the last study visit of Study 124 Part B will not be the same day as the Day 1 Visit of Study 126 (see Section 9.1.1.2.1).
- b Day 1 for subjects in the observational arm can be the last study visit of Study 124 Part B (see Section 9.1.3).
- c The Follow-up OE in the observational arm can be performed in Study 124.
- d Only for subjects who received at least 4 weeks of study drug in Study 124 Part B.

**9.1.1 Ivacaftor Arm**

**9.1.1.1 Ivacaftor Arm: Screening (Subjects Not From Study 124 Part B)**

Subjects not from Study 124 Part B will only be allowed to enroll in Study 126 after an adequate number of subjects have completed the corresponding age cohort in Study 124, in conjunction with feedback from regulatory authorities.

Subjects who participated only in Study 124 Part A and subjects who did not participate in Study 124 will have a Screening Period. *CFTR* genotyping does not need to be repeated for subjects from Study 124 Part A or for subjects whose genotype is adequately documented in their medical record and who receives approval from the Vertex medical monitor (Section 11.6.2).

The investigator (or an appropriate authorized designee at the study site) will obtain informed consent from the subject's parent or legal guardian before any study specific procedures are performed. Screening will occur within 28 days before administration of study drug.

- If serum chemistry and hematology assessments are performed >9 days before Day 1, they must be repeated on Day 1, and the results must be reviewed and eligibility confirmed before the first dose of study drug.
- If an OE was conducted in Study 124 Part A within 12 weeks of the Day 1 Visit, the Day 1 Visit OE does not need to be repeated.

Screening Visit assessments are listed in Table 3-4.

To prepare for study participation, the subject's parent or legal guardian will be instructed on the study restrictions (Section 9.3).

#### **9.1.1.1.1 Repetition of Screening Assessments**

Repetition of screening assessment(s) that do not meet eligibility criteria is not permitted, with the following exceptions:

- There is clear evidence of a laboratory error (e.g., hemolyzed sample) or equipment malfunction. In this case, collection of a repeat sample for the appropriate laboratory test may be permitted after discussion with the Vertex medical monitor or authorized designee.
- If a convincing alternative etiology is identified for elevated transaminases, exclusionary liver function test (LFT) levels may be retested within 2 weeks of the original Screening Visit date with approval of the Vertex medical monitor.
- An adequate slit-lamp examination could not be conducted (Section 11.6.5).

If repeat values are within the eligibility criteria and completed within the screening window or extended screening window (Section 9.1.1.1.3), the subject is eligible for the study.

#### **9.1.1.1.2 Rescreening**

Rescreening may be considered only with approval of the Vertex medical monitor. The investigator (or an appropriate authorized designee at the study site) will confirm the assessments (e.g., number/type of blood sample assessments) required for rescreening with the Vertex medical monitor. *CFTR* genotyping and sweat chloride testing do not need to be repeated and the OE only needs to be repeated if it has been >12 weeks since the last adequate slit-lamp examination.

If a subject is rescreened, the rescreening window (28 days) will begin once the first rescreening assessment has been initiated.

### 9.1.1.1.3 Extension of Screening Window

A subject may have the screening window extended by 2 weeks for the following reasons upon approval by the Vertex medical monitor:

- Repetition of screening assessments (Section 9.1.1.1.1)
- Unexpected operational or logistical delays (e.g., delayed drug shipment)
- Scheduling of the OE (Section 11.6.5)
- Availability of required equipment

A subject may have the screening window extended by 4 weeks upon approval by the Vertex medical monitor for a repeat slit-lamp examination (Sections 9.1.1.1.1 and 11.6.5).

Regardless of approved extensions in the screening window, all subjects to be enrolled in the ivacaftor arm must have Day 1 serum chemistry and hematology assessments performed and reviewed for eligibility within 9 days before dosing on Day 1.

### 9.1.1.2 Ivacaftor Arm Treatment Period (All Subjects)

Ivacaftor will be administered every 12 hours (q12h) from Day 1 through the morning dose of the Week 96 Visit. At each visit, except the final treatment period visit, the ivacaftor dose for each subject will be reassessed and adjusted if necessary. See Section 9.2.2 for information about ivacaftor doses.

Subjects will be outpatients; study visits will occur as follows:

- For subjects from Study 124 Part B: Day 1 and Weeks 12, 24, 36, 48, 60, 72, 84, and 96.
- For subjects not from Study 124 Part B: Day 1 and Weeks 2, 4, 8, 12, 18, 24, 36, 48, 60, 72, 84, and 96; a telephone contact will occur at Day 3.

Treatment Period assessments are listed in Table 3-1 and Table 3-2 for subjects from Study 124 Part B and in Table 3-3 for subjects not from Study 124 Part B.

#### 9.1.1.2.1 Transition from Study 124 Part B to Day 1 of Study 126

All subjects must sign the ICF before any Study 126-related assessments. Subjects from Study 124 Part B can transition into Study 126 as follows:

- **Same-day Transition:** If the Day 1 Visit is the same day as the Week 24 Visit of Study 124 Part B, the subject will not have to perform any Day 1 assessments that were performed at the Week 24 Visit of Study 124 Part B (Table 3-1).
- **Gap Transition:** If the Day 1 Visit is NOT the same day as the last study visit of Study 124 Part B, all Day 1 assessments will need to be performed (Table 3-2), with the possible exception of the following:
  - Clinical laboratory assessments: Results must be reviewed and eligibility confirmed before dosing on Day 1.
    - If the Day 1 Visit is conducted  $\leq 9$  days after the last study visit of Study 124 Part B, the serum chemistry and hematology assessments performed at the last study visit of Study 124 Part B will not need to be repeated.

- If the Day 1 Visit is conducted >9 days after the last study visit of Study 124 Part B, the serum chemistry and hematology assessments must be repeated on Day 1, and the results must be reviewed and eligibility confirmed before the first dose of study drug.
- OE: If an OE was conducted in Study 124 Part B within 24 weeks of the Day 1 Visit, the Day 1 Visit OE does not need to be repeated. Otherwise, an OE must be conducted within 14 days of the Day 1 Visit. Throughout this study, these subjects should have OEs approximately every 24 weeks ( $\pm$  14 days) from the last OE in Study 124.

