**Table 3-2 Schedule of Assessments for VX15-770-126 (Ivacaftor Arm: Gap Transition Subjects From Study 124 Part B)**

Event/Assessment	Treatment Period (Day 1 through Week 96)				ETT Visit a	Safety Follow-up Visit b	24-Week Follow- up OE
	Day -28 to Day -1	Day 1 c	Weeks 12, 36, 60, and 84 (±7 Days)	Weeks 24, 48, 72, and 96 (±7 Days)	As Soon as Possible After the Last Dose	4 Weeks (±7 Days) After the Last Dose	24 Weeks (+ 14 Days) After the Last Dose
Informed consent d	X	X					
Reconfirm eligibility	X	X					
Medical history e	X						
Clinic visit	X	X	X	X	X	X	
Study drug dose determination f		X	X	X			
Length and weight g		X	X	X	X	X	
Physical examination h		X	X	X	X	X	
Vital signs i		X	X	X	X	X	
12-lead ECGs l,j		X		X	X	X	
Serum chemistry and hematology	X k		X	X	X	X	

- a The ETT Visit is to be scheduled as soon as possible after the last dose of ivacaftor. If the ETT Visit occurs 3 weeks or later after the last dose of ivacaftor, the Safety Follow-up Visit will not be required. Subjects who elect to receive commercially available ivacaftor will be discontinued from ivacaftor dosing and will complete the ETT Visit and Follow-up OE.
- b For subjects who elect to receive commercially available ivacaftor, the Safety Follow-up Visit will not be required.
- c The Day 1 Visit will not be the same day as the last study visit of Study 124 Part B. All Day 1 assessments will be conducted on Day 1 with the possible exception of the serum and hematology assessments and the OE, as detailed in footnotes **k** and **m**. If the Day 1 Visit is ≤9 days after the last study visit of Study 124 Part B, the subjects must sign the ICF and confirm eligibility before dosing on Day 1.
- d Subjects must sign the ICF before undergoing any study-related assessments.
- e Medical history only applies to subjects that complete a Study 124 Safety Follow-up Visit and only for new conditions that start after the Study 124 Safety Follow-up Visit and prior to the Study 126 Screening Visit.
- f The ivacaftor dose for each subject will be reassessed based on body weight and adjusted if necessary (see Section 9.4).
- g Length and weight measurements will be performed predose through the Week 24 Visit (see Section 11.5.1).

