**Table 3-2 Schedule of Assessments for VX15-770-126 (Ivacaftor Arm: Gap Transition Subjects From Study 124 Part B)**

Event/Assessment	Day -28 to Day -1	Treatment Period (Day 1 through Week 96)			ETT Visit a	Safety Follow-up Visit b	24-Week Follow-up OE
		Day 1 c	Weeks 12, 36, 60, and 84 (±7 Days)	Weeks 24, 48, 72, and 96 (±7 Days)	As Soon as Possible After the Last Dose	4 Weeks (±7 Days) After the Last Dose	24 Weeks (+ 14 Days) After the Last Dose
Ophthalmologic examination l		X m		X	X n		X
Fecal sample collection o		X		X	X		
Sweat chloride test p		X		X			
Qualitative microbiology cultures		X		X			
Multiple breath washout (optional) q		X		X r			

k If the Day 1 Visit is conducted ≤9 days after the last study visit of Study 124 Part B, the serum chemistry and hematology assessments performed at the last study visit of Study 124 Part B will not need to be repeated. If the Day 1 Visit is conducted >9 days after the last study visit of Study 124 Part B, the serum chemistry and hematology assessments can be obtained up to 9 days before or at the Day 1 Visit. The results must be reviewed before the first dose of study drug.

l The OE will be conducted by a licensed ophthalmologist, preferably a pediatric ophthalmologist. The OE may be performed at the study visit or ± 14 days of the clinic visit.

m The OE does not need to be repeated if the subject had an OE in Study 124 Part B within 24 weeks of the Day 1 Visit. Otherwise, an OE must be conducted within 14 days of the Day 1 Visit. Throughout this study, these subjects should have OEs approximately every 24 weeks (± 14 days) from the last OE in Study 124.

n The OE for the ETT Visit will be conducted for all subjects who prematurely discontinue ivacaftor dosing (for any reason) unless performed in the last 12 weeks.

o Samples will be analyzed for fecal elastase-1 and other markers of intestinal inflammation, including fecal calprotectin. Samples may be collected (e.g., at home) up to 24 hours before the study visit (e.g., at home) and brought to the clinic. If the sample is collected in the clinic, the sample may be collected pre- or postdose.

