### 8.1 Ivacaftor Arm: Subjects From Study 124 Part B

#### 8.1.1 Inclusion Criteria

1. Subjects transitioning from Study 124 Part B must have completed the last study visit of Study 124 Part B

Added guidance:

- Subjects who had a study drug interruption at the last scheduled visit of Study 124 Part B, subjects who required study drug interruption that was to be continued or initiated at Day 1 in Study 126, or subjects who resumed study drug in Study 124 Part B after a study drug interruption due to elevated transaminases but who did not complete at least 4 weeks of rechallenge with study drug (due to the timing of the rechallenge versus the time remaining in Study 124 Part B) must meet eligibility criteria and have received approval from the Vertex medical monitor.
2. For Gap Transition subjects: hematology and serum chemistry results at baseline with no clinically significant abnormalities that would confound the study assessments or pose an additional risk to administering ivacaftor to the study subject, as judged by the investigator.
  3. As judged by the investigator, parent or legal guardian must be able to understand protocol requirements, restrictions, and instructions; and must sign the informed consent form (ICF).

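### For the probably very few Gap Transition subjects whose last Part B lens examination is more than 24 weeks old, ivacaftor may be restarted up to 14 days before the required entry examination: a minor gap that is cheap to close

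*Protocol*

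**What the plan says.** Section 9.1.1.2.1 and Table 3-2 cover children who leave Study 124 Part B and start Study 126 on a later date (Gap Transition). If they had a Part B OE in the 24 weeks before Day 1, no entry OE is needed. If not, the rule is "Otherwise, an OE must be conducted within 14 days of the Day 1 Visit". Footnote m of Table 3-2 repeats it, and so does SAP Table 11-2.

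Other text bears on the direction of that window:

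- Table 3-2 footnote l: "The OE may be performed at the study visit or ± 14 days of the clinic visit".
- Table 3-2 footnote c: "All Day 1 assessments will be conducted on Day 1 with the possible exception of the serum and hematology assessments and the OE".
- Section 9.1.1.2: "Ivacaftor will be administered every 12 hours (q12h) from Day 1 through the morning dose of the Week 96 Visit".

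Blood tests for the same children are handled differently. Section 9.1.1.2.1 states "Clinical laboratory assessments: Results must be reviewed and eligibility confirmed before dosing on Day 1", and Section 8.1.1 has an inclusion criterion that begins "For Gap Transition subjects: hematology and serum chemistry results at baseline with no clinically significant abnormalities".

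For later monitoring, Section 9.1.1.2.1 says "Throughout this study, these subjects should have OEs approximately every 24 weeks", with a tolerance of 14 days either way, counted from the last Study 124 OE. Section 11.6.5 requires dosing to stop if any OE in the ivacaftor arm shows a new opacity or cataract.

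**The concern.** OEs are part of the primary safety endpoint. Section 9.2.3 explains that they were added because young rats dosed with ivacaftor developed lens opacities. By requiring an entry OE, the plan itself treats the lens examination as due for these children, yet it lets drug be restarted first. A child with an opacity that arose since the last Part B OE could be dosed for two weeks before a finding that would have stopped treatment. An opacity first seen on Day 15 also could not be dated as before or after the restart.

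The other entry rules do not close the gap. The lens exclusions (8.2.2 #11 and #12) apply to subjects not from Part B. Section 11.6.5 withholds enrolment until an adequate slit-lamp examination, but only during screening. The synopsis limits the Screening Period to subjects not from Part B. Table 3-2 does have a Day -28 to Day -1 column, but its OE row is marked under Day 1. Section 8.1.2 has no lens criterion, only the general investigator-judgement exclusion.

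**Working it through.** **Direction of the window.** Where Table 3-2 means an assessment to come first, it says so. Footnote k allows that "the serum chemistry and hematology assessments can be obtained up to 9 days before or at the Day 1 Visit" and adds that results are reviewed ahead of the first dose. Footnote q places a Day 1 multiple breath washout in the week preceding the visit. Footnote m has no such limit, and footnote l is two-sided. An entry OE after the first dose is therefore permitted, though not required.

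**Inputs from the documents.** Waiver limit 24 weeks; entry OE window 14 days; dosing every 12 hours from Day 1; routine spacing 24 weeks ± 14 days; SAP Table 11-4 OE windows for rollover subjects.

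**Calendar time and doses**

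- Waiver limit: 24 × 7 = 168 days.
- Latest entry OE: Day 1 + 14 = Day 15.
- Doses before the Day 15 morning dose: 14 × 2 = 28.
- Age of the last Part B OE: more than 168 days at the first dose, and more than 168 + 14 = 182 days on Day 15.
- Routine spacing: 168 − 14 = 154 to 168 + 14 = 182 days.

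In calendar time, the smallest overrun lies just past the routine limit. Neither 8.1.1 nor 9.1.1.2.1 caps the gap, so there is no upper bound.

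**Drug-exposed time.** The Study 124 OE schedule is not in these documents, so this step is an assumption shown over a range. It takes Part B treatment as about 24 weeks (168 days), since Week 24 is the Part B visit from which same-day transition occurs, and assumes no ivacaftor during the gap. Let *d* be the days from the last Part B OE to the last Part B dose. The entry OE is triggered when the gap exceeds 168 − *d* days. Exposed days between OEs by Day 15 are *d* + 14, and doses are twice that.

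| Last Part B OE | *d* | Gap that triggers the entry OE | Exposed days by Day 15 | Doses |
|---|---|---|---|---|
| At end of Part B treatment | 0 | > 168 days | 14 | 28 |
| 84 days earlier | 84 | > 84 days | 98 | 196 |
| At Part B baseline (extreme) | 168 | > 0 days | 182 | 364 |

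The extreme case equals the routine limit of 182 days. A continuously treated child examined at that limit would also have had 182 × 2 = 364 doses between OEs.

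**Effect on the analysis.** In SAP Table 11-4 the rollover OE baseline is the parent-study value, and Week 24 (target Day 168) covers Days 2 to 252. An entry OE on Days 2 to 15 is therefore labelled Week 24, although it lies 168 − 15 = 153 to 168 − 2 = 166 days before the target. Under SAP 8.1 the safety record nearest the target is used, so a later Week 24 OE displaces it unless dosing stops early. SAP 8.4.6 summarises cataract or opacity as a categorical incidence. Read as a per-subject summary, that count is unaffected by the visit label.

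**The case against.** The strongest reply is that the hazard follows drug exposure, and the gap is largely time off drug. The table supports this: exposed time between OEs stays about within the spacing that the plan accepts for every treated child. This stands, and it is the main reason the point is minor.

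Second, the 14 days match the routine tolerance. A child whose last OE was exactly 168 days before Day 1 is waived and may be examined on day 182, which is also Day 15. Under a pre-dose rule, a child at 169 days would have to wait. That is fair, but the plan already draws a line at 168 days by requiring an entry OE beyond it.

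Third, the contrast with laboratory tests may be deliberate: blood results are an entry criterion, while for previously treated children the OE is periodic monitoring. That is a reasonable reading. Still, a new opacity is a mandatory stop, so looking before the restart gains something at little cost.

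Fourth, the subset may be almost empty. Table 3-4 footnote b and Section 9.1.4 show that an OE about 24 weeks after the last dose could be done in Study 124, which could reset the clock. Those passages concern the observational arm, so the support is indirect. Prior Part B OEs, ocular history collected by Day 1 (11.6.5) and investigator judgement under 8.1.2 also offer some protection.

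None of these supplies a rule that places the OE before the first dose.

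**Conclusion.** The point holds as a minor safety gap. For Gap Transition subjects without a recent Part B OE, the text permits up to 14 days and 28 doses before the lens is re-examined.

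A reader might infer two stronger things that the documents do not support. The first is that the uncapped gap leaves children on drug without monitoring for an unlimited period. The uncapped part is largely off drug, and exposed time reaches about 182 days at most under the stated assumptions. The second is that cataract incidence is biased. A finding on Day 15 still counts for that child and still stops dosing; only the visit label is wrong.

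The size rests on about 24 weeks of Part B treatment, no ivacaftor in the gap, and a subset that is probably very small. Its number is not given. This is a low-priority improvement worth making because it is cheap.

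**What to change.** 1. In 9.1.1.2.1 and Table 3-2 footnote m, and in SAP Table 11-2, replace the sentence with: *If not, the OE is to be done on Day 1 or in the 14 days preceding it, and its result reviewed ahead of the first Study 126 dose; the + 14 days in footnote l does not extend to this OE.*
2. In 8.1.2, for these subjects, add an exclusion for a new lens opacity or cataract at this OE, mirroring 8.2.2 #12 and its allowance for congenital, nonprogressive findings. Without it, a pre-dose finding would have no explicit consequence for eligibility.
3. In SAP Table 11-4, report this OE under its own nominal entry visit and not as Week 24. The row is needed in either case, since an OE on or before Day 1 currently has no place there.

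The cost is small. The examination is already required, and 14 days fit inside the Day -28 to Day -1 column of Table 3-2. The only downside is that Day 1 may wait for the ophthalmology appointment. A child excluded on this OE is documented like any other subject who is not enrolled (13.1.1.3); no extra CRF collection is proposed. The SAP cites an administrative letter of October 2022, so if enrolment has closed, items 1 and 2 matter mainly for later use. Item 3 still applies to the final analysis.
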